10.1.1 Confinement, Return Visits, and Follow-Up

Patients will be admitted to the CRU on Day -8, at the time indicated by the CRU, until after completion of study procedures on Day 3 as indicated in the Study Events Flow Chart ([Section 6](#)). At all times, a patient may be required to remain at the CRU for longer at the discretion of the PI or designee.

All patients who receive the study drug or matching placebo (including patients who terminate the study early) will return to the CRU on Day 14 (\pm 2 days) for coagulation tests, immunogenicity sample collection, and to determine if any AE has occurred since the last study visit.

10.1.2 Study Duration

The total planned duration of patient participation is approximately 50 days from screening to follow-up.

10.2 Study Conduct

See the Study Events Flow Chart for a summary of the schedule of study participation and procedures in [Section 6](#). The end of the study is defined as the date of the last scheduled study procedure as outlined in the Study Events Flow Chart ([Section 6](#)).

11. STUDY POPULATION

11.1 Inclusion Criteria

Patients must fulfill all of the following inclusion criteria to be eligible for participation in the study:

1. ESRD maintained on stable outpatient HD regimen, using an established (> 3 months) and normally functioning, regular flow, uninfected mature AV fistula (or AV graft) and skin consistent with standard chronic HD access injuries, and HD stability defined as $Kt/V \geq 1.2$ within 3 months prior to screening at a healthcare center for > 3 months from screening.
2. On HD regimen at least 3 times per week for a minimum of 3 hours per dialysis session, using a complication-free well maintained AV fistula (or AV graft), expected and plan to continue this throughout and for at least 3 months beyond the study.
3. Is capable of understanding the written informed consent, provides signed and witnessed written informed consent and agrees to comply with protocol requirements and study-related procedures.

4. Willing to be confined to the CRU for the duration of the study, able to comply with all study-related requirements, and able to adhere to study restrictions and visit schedules.
5. Male or female, between 18 and 80 years of age (inclusive) at the time of screening.
6. BMI of ≥ 18 at the time of screening.
7. Considered by the PI to be clinically stable with respect to underlying ESRD, based on the medical evaluation that includes medical and surgical history, and a complete physical examination including vital sign measurements, ECGs, and clinical laboratory and coagulation test results at screening. Repeat assessments are permitted for any laboratory, coagulation, ECG, or vital sign parameter required for enrollment.
8. Female patients must be of non-childbearing potential and must have undergone one of the following sterilization procedures at least 6 months prior to dosing:
 - hysteroscopic sterilization;
 - bilateral tubal ligation or bilateral salpingectomy;
 - hysterectomy;
 - bilateral oophorectomy;or be postmenopausal with amenorrhea for at least 1 year prior to dosing and follicle-stimulating hormone (FSH) serum levels consistent with postmenopausal status as per PI or designee judgment.
9. Male patients must either be sterile (vasectomy with history of a negative sperm count following the procedure); practice total abstinence from sexual intercourse as the preferred lifestyle (periodic abstinence is not acceptable); use a male condom with any sexual activity; or agree to use a birth control method considered to be appropriate by the Investigator from the time of dosing until 90 days after study drug administration. Male patients must agree not to donate sperm for a period of 90 days after study drug administration.

11.2 Exclusion Criteria

Patients must not be enrolled in the study if they meet any of the following criteria:

1. Documented history of acute vasoocclusive thrombotic event (acute coronary syndrome, stroke or transient ischemic attack, venous thromboembolic event), or vascular access fistula or AV graft failure in the past 3 months.
2. With the exception of unfractionated heparin during HD that is allowed until study check-in, concomitant or prior use of anticoagulant/antiplatelet agents (e.g., low molecular weight heparins, warfarin, apixaban, bivalirudin, ticagrelor, edoxaban, dabigatran, rivaroxaban, clopidogrel, prasugrel, ticlopidine, eptifibatide, tirofiban, dipyridamole, diclofenac, and all other non steroid antiinflammatory drugs) that may affect hemostasis for 2 weeks prior to check-in on Day -8 and throughout the study.

3. Any clinically significant (CS) concomitant disease or condition (including treatment for such conditions) that, in the opinion of the PI, could either interfere with the study drug, compromise interpretation of study data, or pose an unacceptable risk to the patient.
4. Any other CS abnormalities in laboratory test results at screening or Day -8 check-in that would, in the opinion of the PI, increase the patient's risk of participation, jeopardize complete participation in the study, or compromise interpretation of study data.
5. Pregnant (positive pregnancy test) at screening or check-in on Day -8. If serum human chorionic gonadotropin (hCG) pregnancy test results are indeterminate, follow-up testing should be performed to determine eligibility.

All female patients will not be pregnant and will have a negative pregnancy test at screening and check-in on Day -8, with the following exception: females receiving dialysis with an indeterminate pregnancy test result or persistently low hCG resulting in a false positive pregnancy test may be included in the study at the discretion of the PI. Postmenopausal patients with a result outside the postmenopausal range or an indeterminate pregnancy test will undergo additional testing with FSH to confirm postmenopausal status prior to study enrollment.

6. Treatment with another investigational drug or participation in a device study within 30 days (or 5 half-lives, whichever is longer) prior to check-in on Day -8.
7. Acute illness that is considered by the PI to be CS within 2 weeks of check-in on Day -8.
8. Surgery within the past 90 days prior to dosing which in the opinion of the PI or designee is clinically relevant.
9. Currently have established underlying inherited or acquired symptomatic bleeding disorders and/or are at risk for excessive bleeding per PI judgment or current active bleeding (e.g., gastrointestinal, intracranial), aside from minor bleeding from the puncture site on the AV fistula or AV graft, which would be expected to occur during the dialysis procedure, with the following values:
 - Platelet count < 100,000 cells/mm³ (if < 100,000 cells/mm³ but > 75,000 cells/mm³, with permission of PI and medical monitor) at screening or check-in on Day -8
 - INR > 1.4 at screening or check-in on Day -8
 - aPTT up to 1.2 x upper limit of normal (ULN) (if > 1.2 x ULN and up to < 1.5 x ULN, with permission of PI and medical monitor) at screening or check-in on Day -8
 - Alanine aminotransferase (ALT) or aspartate aminotransferase (AST) > 2 x ULN at screening or check-in on Day -8
 - Total bilirubin > 1.2 x ULN at screening or check-in on Day -8
10. Seated blood pressure < 90/40 mmHg at screening and check-in on Day -8.
11. Exclusion criteria for ECG at screening and check-in on Day -8:

Heart rate	< 45 and > 110 bpm
QTcF interval	> 500 msec
bpm = beats per minute; msec = milliseconds; QTcF = QT interval corrected using Fridericia's formula	

- Any significant arrhythmia or conduction abnormality, (including but not specific to atrioventricular block [2nd degree or higher], Wolff Parkinson White syndrome [unless curative radio ablation therapy]), which, in the opinion of the PI and Medical Monitor, could interfere with the safety for the individual patient.
- Non-sustained or sustained ventricular tachycardia (> 2 consecutive ventricular ectopic beats at a rate of > 1.7/second).

12. History of a CS allergy or a known sensitivity or idiosyncratic reaction to any compound known to be present in E-WE thrombin, its related compounds, or any compound listed as being present in the study formulation.
13. Hypersensitivity to β -lactam / penicillin derivatives.
14. Participate in strenuous exercise from 72 hours prior to check-in on Day -8 and throughout the study.
15. Positive test for drugs of abuse and/or positive alcohol test at screening or check-in on Day -8 if not accounted for by a prescription medication. Patients with a positive test based on a prescribed medication may be enrolled.
16. Positive test at screening for hepatitis B surface antigen (HBsAg) or human immunodeficiency virus (HIV). If a patient with ESRD has positive test results for hepatitis C virus (HCV) but liver function tests are otherwise not clinically significant, the patient may be included at the PI's discretion.
17. Receiving blood purification therapy other than HD.
18. Donation of blood or significant blood loss within 56 days prior to dosing.
19. Plasma donation within 7 days prior to dosing.
20. Presence of advanced malignant neoplasms of any organ or system that produces illness or symptoms that have been treated within 3 months with chemotherapy or whole body irradiation, or bone marrow irradiation, and may affect life expectancy in the following 6 months.
21. Any other reason that would render the patient unsuitable for study enrollment at the discretion of the PI.

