1. PROTOCOL REVISION HISTORY

DATE/NAME	DESCRIPTION												
22April2020 by [name]	
Final Protocol, Amendment 2:
 
This protocol was amended to update exclusion criterion #9 in order to aid in recruitment. Cut--off values for hemoglobin entry levels is not required for this study's population (patients with end-stage renal disease). Removal of this criterion will not affect patients safety upon drug administration and will not interfere with study endpoints.
 
Therefore, the last bullet in Section 11.2 Exclusion Criteria, criterion # 9, "Hemoglobin concentration < 10 g/dL at screening or check-in on Day -8" was removed.
 
In addition, the protocol clarification dated February 12, 2020 was incorporated in this amendment. In Section 13.5.1 Blood Sampling and Processing and in Section 13.7.1 Protein C Analysis, allowable time deviation window for post-dose blood collections were thus added.
												
01May2019 by [name]	
Final Protocol, Amendment 1:
 
This protocol was amended at the Sponsor's request to add sample timepoints for protein C in order to characterize protein C in all hemodialysis sessions. Additional samples will be collected at the start and at the end of hemodialysis on Days -7, -5, -2, and 3. Thus the total number of time points for protein C analysis sample collection will increase from 8 to 16:
 
In Section 6 – Study Event Flow Chart, collection of blood samples for protein C analysis were added at the start and the end of hemodialysis on Days -7, -5, -2, and 3.
 
In Section 13.8 - Blood Volume for Study Assessments, Table 3 - Blood Volume during the Study, was amended as follows (deleted text in strike-through and added text in bold in a condensed version of the table):
 
  
 Sample Type	Number of Time Points	Approximate Volume per Time Point * (mL)	Approximate Sample Volume Over Course of Study (mL)	
   
 Blood for protein C (ships to Aronora)	816	2	1632	
 
 Total Blood Volume (mL)→	Up to 220236***	
  
	Sample Type	Number of Time Points	Approximate Volume per Time Point * (mL)	Approximate Sample Volume Over Course of Study (mL)	Blood for protein C (ships to Aronora)	816	2	1632	Total Blood Volume (mL)→			Up to 220236***

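### In exclusion criterion 9 the aPTT bullet runs opposite to its own parenthesis and the other laboratory bullets, gives no explicit rule at or above 1.5 x ULN, and follows a lead-in that leaves the scope of all the laboratory limits unclear

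*Protocol*

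**What the plan says.** Protocol section 11.2 opens with "Patients must not be enrolled in the study if they meet any of the following criteria", so whatever is listed beneath it is a reason to keep a patient out.

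Criterion 9 begins with a clinical condition: "Currently have established underlying inherited or acquired symptomatic bleeding disorders and/or are at risk for excessive bleeding per PI judgment or current active bleeding". After setting aside minor puncture-site bleeding it continues "which would be expected to occur during the dialysis procedure, with the following values", and five laboratory bullets follow. Each is checked at screening or at check-in on Day -8:

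- Platelets: "Platelet count < 100,000 cells/mm³ (if < 100,000 cells/mm³ but > 75,000 cells/mm³, with permission of PI and medical monitor".
- INR: "INR > 1.4 at screening or check-in on Day -8".
- aPTT: "aPTT up to 1.2 x upper limit of normal (ULN) (if > 1.2 x ULN and up to < 1.5 x ULN", in which case permission is needed from the investigator and the medical monitor.
- ALT or AST above 2 x ULN.
- Total bilirubin above 1.2 x ULN.

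A sixth bullet, on hemoglobin, was removed by Amendment 2. The Protocol Revision History explains the removal by saying "Cut--off values for hemoglobin entry levels is not required" for this population.

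No other section of the protocol or SAP gives a numerical aPTT limit for entry. Four provisions leave room for investigator judgment: inclusion 7 (clinical stability, judged partly on screening coagulation results), exclusion 3 (significant concomitant conditions), exclusion 4 (other clinically significant laboratory abnormalities) and exclusion 21 (any other reason).

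**The concern.** There are two separate defects in one criterion.

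The first is direction. In a list of disqualifying values, four bullets state the abnormal side and the aPTT bullet states the acceptable side. Its parenthesis then lets in higher values with permission, which makes no sense if lower values are barred. The wording also stops at 1.5 x ULN and does not say what happens there or beyond.

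The second is scope. The words that introduce the bullets can be read as qualifying the bleeding condition or as introducing limits that apply to everyone. The two readings give different answers for the same patient.

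What is at stake is an operative safety entry rule, not background text. aPTT is the coagulation test that the protocol reports as rising with dose in healthy subjects (8.2.2.2) and as prolonged beyond the reference range at high doses in toxicology studies (8.2.1.3). Section 8.4 says that the drug's hemostatic safety in this population is not yet known. Coagulation tests and access-site bleeding time are among the primary outcome measures (9.2). SAP Appendices 16.2.5.1 and 16.2.5.2 list eligibility by patient, and a criterion that contradicts itself cannot be programmed or audited consistently.

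**Working it through.** No sample size, power or error rate is involved, so there is no plan figure to reproduce. The check applies criterion 9 to a set of illustrative values under each reading.

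**Inputs.** The header of section 11.2 (meeting an item means no enrollment), the criterion 9 lead-in, the aPTT bullet, and the platelet bullet as comparator. All are in Protocol 11.2. The test values are chosen only to fall on each side of the stated boundaries. The joined reading assumes that meeting any one bullet is enough.

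**Rule as written for aPTT, with x in multiples of ULN.**

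- x ≤ 1.2: named by the bullet, therefore excluded.
- 1.2 < x < 1.5: may enter with permission.
- x ≥ 1.5: not named.

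| aPTT (x ULN) | Bullets stand alone | Bullets joined to lead-in, bleeding condition present | Bullets joined to lead-in, no bleeding condition |
|---|---|---|---|
| 0.8 | excluded | excluded | not excluded by criterion 9 |
| 1.0 | excluded | excluded | not excluded by criterion 9 |
| 1.2 | excluded | excluded | not excluded by criterion 9 |
| 1.3 | permission | permission | not excluded by criterion 9 |
| 1.49 | permission | permission | not excluded by criterion 9 |
| 1.5 | no aPTT rule | no aPTT rule | not excluded by criterion 9 |
| 2.0 | no aPTT rule | no aPTT rule | not excluded by criterion 9 |

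Wherever the bullet operates, the lowest values are barred and the highest meet no rule. The inversion therefore does not depend on how the lead-in is read.

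**Comparator: the platelet bullet, read alone (cells/mm³).**

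| Platelet count | Result |
|---|---|
| 150,000 | not excluded |
| 100,000 | not excluded |
| 90,000 | permission |
| 75,000 | excluded |
| 60,000 | excluded |

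Here the permission band (above 75,000 and below 100,000) lies inside the excluded range, and everything beyond the band is excluded. The aPTT band lies outside the range that its bullet names, and nothing is said beyond it.

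**Scope of the lead-in.** The last column of the aPTT table holds for the other bullets too. On the joined reading, a patient with no bleeding condition is not excluded by criterion 9 at any aPTT, platelet, INR, ALT/AST or bilirubin value. On the stand-alone reading each limit applies to everyone. Two indications favor the stand-alone reading. ALT/AST and bilirubin are liver tests that sit oddly as qualifiers of a bleeding condition. Amendment 2 also calls the removed hemoglobin bullet an entry-level cut-off and says it was removed to help recruitment, which fits a limit acting on its own. The amendment log is used here only as evidence of intent; the ambiguity is in the current text.

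**The case against.** The best defense is that the intent can be recovered from the bullet itself. A permission requirement above 1.2 x ULN makes sense only if values up to 1.2 x ULN need no permission, and no site would plausibly turn away every patient with a normal aPTT. That stands as an account of intent and of likely conduct. It does not supply a rule at 1.5 x ULN or above, and it does not settle the lead-in.

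Several stronger readings are tempting, and the documents do not support them.

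- A reader might infer that criterion 9 both excludes every patient with a normal aPTT and ties every limit to a bleeding condition. The first needs the bullets to stand alone and the second needs them joined to the lead-in. They are alternatives and cannot be added together.
- A reader might infer that nothing keeps out a patient with a very high aPTT. What is missing is an explicit numerical rule. Inclusion 7 and exclusions 3, 4 and 21 still allow the investigator to decline such a patient. They are discretionary, and none carries the joint investigator and medical-monitor permission that the bullet requires for lower values, so they soften the consequence without curing the wording.
- A reader might infer that a patient with low platelets or a high INR but no declared bleeding disorder always escapes criterion 9. The lead-in also covers investigator-judged risk of excessive bleeding and current active bleeding, so such a patient can be brought within it without a diagnosed disorder.
- A reader might infer that the wrong patients were enrolled. The documents show what the text says, not how it was applied.

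**Conclusion.** Criterion 9 is wrong as written. The aPTT bullet contradicts its own parenthesis and runs opposite to the four other laboratory bullets. Taken as a stand-alone exclusion it bars values up to 1.2 x ULN, permits values above 1.2 and below 1.5 x ULN with permission, and has no explicit rule from 1.5 x ULN upward, where only investigator discretion remains. Separately, it is unclear whether all five laboratory bullets apply to every patient or only to those with a bleeding disorder, judged bleeding risk or active bleeding; the Amendment 2 wording points to the former but does not settle it.

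This is most likely a drafting error. The finding rests on the current wording of section 11.2 and on the absence of any other numerical aPTT entry limit in either document. It does not rest on any claim about how the site behaved, and it does not bear on the planned estimates or the number of patients.

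**What to change.** The sponsor should amend criterion 9 in three respects:

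1. Reconcile the direction of the aPTT bullet with its own parenthesis and with the form of the parallel bullets.
2. State how aPTT values at or above 1.5 x ULN are handled.
3. State whether the laboratory limits apply independently of the bleeding condition in the lead-in or only together with it.

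The third step is needed even if the first two are made, because correcting the aPTT direction leaves the lead-in ambiguous for all five bullets. The clinical team sets the limits and chooses the scope; none is proposed here.

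The cost is a short text amendment. The sample size of 36, the analysis populations and the planned summaries stay as they are.

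### The heart-rate limit in exclusion criterion 11 cannot be met as printed, and criteria 10 and 11 leave open whether an abnormal value at check-in alone excludes

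*Protocol*

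**What the plan says.** Protocol Section 11.2 opens with the rule that one criterion is enough: "Patients must not be enrolled in the study if they meet any of the following criteria". The wording at issue is in two criteria.

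- Criterion 10 reads "Seated blood pressure < 90/40 mmHg at screening and check-in on Day -8".
- Criterion 11 begins "Exclusion criteria for ECG at screening and check-in on Day -8". A small table follows, with a heart-rate row, "< 45 and > 110 bpm", and a QTcF row (above 500 msec). Two rhythm and conduction items come after the table.

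Other criteria in the list that name the same two visits join them differently. Criterion 4 has "Any other CS abnormalities in laboratory test results at screening or Day -8 check-in", criterion 15 has "positive alcohol test at screening or check-in on Day -8", and all five laboratory values in criterion 9 follow the pattern of "INR > 1.4 at screening or check-in on Day -8". Criterion 5 excludes for a positive pregnancy test at either visit.

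The flow chart (Protocol Section 6) schedules the inclusion/exclusion review, the ECG and vital signs at screening and again on Day -8. Screening may take place up to 28 days before Day -8.

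**The concern.** An exclusion criterion works only if a patient can meet it. The heart-rate row describes two excluded ranges but joins them so that a patient would have to be in both at once. Taken at its word, a patient with a heart rate of 120 bpm breaches no numeric limit.

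The visit wording raises a second question. Where the list says *or*, an abnormal value at either visit excludes. Where it says *and*, a site could fairly conclude that the abnormality must be present twice. The case that matters is a patient who is acceptable at screening and abnormal on Day -8. That visit is the last scheduled eligibility review, and SAP Section 7.7 schedules no further ECG until half an hour after dosing starts.

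ECGs and vital signs are among the primary outcome measures (Protocol Section 9.2). The SAP also lists eligibility by criterion not met at screening (Appendix 16.2.5.1) and continued eligibility at check-in (Appendix 16.2.5.2). Both listings, and any deviation recorded against them, depend on what the criteria mean.

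**Working it through.** The plan gives no figure to reproduce here; the check is logical.

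**Heart rate.** Input: the printed row in criterion 11. Count the whole-number rates from 0 to 300 bpm (301 values) that meet each version.

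- Below 45 *and* above 110: the ranges do not overlap, so 0 of 301.
- Below 45 *or* above 110: 45 values (0 to 44) plus 190 values (111 to 300), so 235 of 301.

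These are counts of possible values, not of patients. They show only that the printed condition is empty.

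**Visits.** Inputs: criterion 10 and the lead-in to criterion 11. The two readings give:

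| Abnormal at screening | Abnormal at check-in | Excluded if both visits are needed | Excluded if either visit is enough |
|---|---|---|---|
| No | No | No | No |
| No | Yes | No | Yes |
| Yes | No | No | Yes |
| Yes | Yes | Yes | Yes |

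The readings differ whenever exactly one visit is abnormal, which includes the check-in-only case.

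The two criteria do not stand on the same footing. In criterion 10 the *and* is inside the condition itself, so the literal meaning is low pressure at both visits. In criterion 11 it is in the line that introduces the table. That line can be read as naming the visits at which the limits apply (each visit) or as requiring the abnormality at both. The QTcF row contains no visit wording of its own.

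Criterion 5 shows that the section can use the two words with different meanings. A positive pregnancy test excludes at screening *or* check-in, while the required negative test must be present at screening *and* check-in. Read the same way, criterion 10 does not exclude a patient who is low only on Day -8.

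**Systolic and diastolic.** Criterion 10 gives a pair, 90/40. A reading of 85/60 is below the first number and not the second. Combined with the visit question, there are 2 × 2 = 4 readings of criterion 10. For a patient with a normal pressure at screening:

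- 85/60 on Day -8 excludes under one of the four (either visit, either component).
- 85/38 on Day -8 excludes under two of the four (either visit, with either component or both).

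**The case against.** The strongest reply is that nobody will apply the heart-rate row literally. Because the literal reading is impossible, a site will take it as two excluded ranges. That is probably true, and it means the practical effect on enrolment may be small. It does not make the text right: staff would have to override a printed limit in order to apply it.

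The second reply is that other safeguards exist, and this largely stands.

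- Criterion 3 lets the investigator exclude for a clinically significant condition, and criterion 21 covers "Any other reason that would render the patient unsuitable for study enrollment at the discretion of the PI".
- The investigator or a designee reviews every ECG tracing (Protocol Section 13.2.4).
- Vital signs are taken again before dialysis on Days -7, -5, -2 and 1, so check-in is not the last look at blood pressure before dosing.
- Protocol Section 11.3 allows a patient to be discontinued for a medical condition that carries substantial risk.

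A reader might therefore be tempted to say that a patient with a QTcF of 520 ms or a pressure of 85/38 on Day -8 alone meets no stated exclusion. The documents do not support that, because the discretionary criteria remain available. They are, however, matters of judgment, whereas criteria 10 and 11 set numeric limits. The repeat assessments allowed under inclusion criterion 7 neither repair an impossible condition nor settle which visits count.

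The third reply is that low pressure at both visits is a coherent rule and may be intended. The documents do not say. That is a reason to ask the sponsor to settle the wording, not to assume the answer.

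**Conclusion.** The heart-rate limit in criterion 11 is wrong as written: as a numeric rule it excludes nobody. This rests on the printed text alone. Criterion 10, read literally, requires a low pressure at both visits and is unclear on systolic versus diastolic. The lead-in to criterion 11 is ambiguous on visits. Both sit badly with the *or* wording of criteria 4, 5, 9 and 15.

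Three stronger conclusions might be drawn and should not be.

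- **That a QTcF above 500 msec at check-in alone does not exclude.** Reading the lead-in as applying at each visit is natural, and on that reading it does exclude. The point is ambiguity only.
- **That an ineligible tracing must become the ECG baseline.** SAP Section 7.7 takes the result closest before the dose, including unscheduled ones, so a later repeat ECG would replace it. The footnote to SAP Table 14.3.5.8 does name Day -8. The vital-sign baseline is the last result before the Day 1 dose (SAP Section 7.5), so it would not normally be the check-in value.
- **That a given share of candidates would be wrongly admitted.** The documents give no rate of abnormal values and no correlation between visits, so no such percentage can be supported.

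The eligibility wording applies equally to both arms and the safety analysis is descriptive, so no treatment comparison is biased by it. The correction is still worth making, because these are operative safety limits and the change costs very little.

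**What to change.** In criterion 11, state the two excluded heart-rate ranges separately, as alternatives, and leave both thresholds as they are.

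For criteria 10 and 11, the sponsor should reconcile the visit wording with the rest of Section 11.2 and say explicitly how a value abnormal only on Day -8 is handled. Criterion 10 should also state whether systolic, diastolic or both must be below the limit. Those choices belong to the sponsor and the investigator; what matters for the analysis is that only one reading remains.

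The cost is a few words in an amendment. Amendment 2 already edited criterion 9 in this section, so the route exists. The possible downside is a few more screen failures at check-in, if the clarified wording makes an abnormal value at either visit sufficient.
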